## APPENDIX X: AMC DATA AND SAFETY MONITORING PLAN

Version 4.0 • September 13, 2010

### Monitoring the Progress of Trials and the Safety of Participants

All AMC protocols that collect safety data follow the *National Cancer Institute (NCI), Cancer Therapy Evaluation Program (CTEP) Guidelines: Adverse Event Reporting Requirements* (<http://ctep.cancer.gov/guidelines/index.html>). All adverse events that meet the NCI's expedited reporting requirements are reported to the Investigational Drug Branch (IDB) of the NCI via the Adverse Event Expedited Reporting System (AdEERS) web application. All expedited adverse event reports are also required to be submitted to the local Institutional Review Board (IRB) of the reporting institution. If NCI holds the IND or no IND is required for a study, the AMC site reports serious adverse events directly to the AMC Operations and Data Management Center (ODMC) via AdEERS. In some instances, the AMC sites may report serious adverse events directly to a commercial sponsor holding the IND, who will then report the event to the AMC ODMC. Most AMC protocols require sites to report all serious adverse events via AdEERS and the AMC ODMC to forward a copy of the report to the sponsor. The AMC ODMC also distributes all IND safety reports to all investigators upon receipt, and makes these reports available on the password-protected section of the AMC Operations web site. Unless an AMC protocol specifies an alternate plan for the review and submission of serious adverse events, all serious adverse events received by the AMC ODMC will be reviewed by the AMC Medical Monitor at the AMC ODMC prior to submission to NCI and the sponsor. For protocols for which the IDB does not have an assigned drug monitor to review serious adverse event reports, in the event of disagreement between the reporting physician and the AMC Medical Monitor regarding the attribution of the event to the investigational agent(s) (i.e., determination of whether the relationship is unrelated, unlikely, possible, probable, or definite), the AMC Medical Monitor will provide the final determination of the relationship.

The AMC ODMC provides listings of all reported adverse events and serious adverse events to the Protocol Chair and Co-chair(s) for review on a regular basis. The AMC ODMC compiles these events in a tabular format and posts them on the password-protected section of the AMC web site where these reports are updated nightly. The AMC web site is accessible to all AMC investigators, co-investigators, and their staff. Email notification that this information is available on the web site will be sent to all site PIs. It is the responsibility of each site to provide this information to their respective IRBs, if required by their IRB. For blinded studies, the serious adverse events are reviewed and tabulated without treatment assignment. The AMC Medical Monitor will review listings of all reported adverse events on a quarterly basis for safety concerns.

Accrual summaries for each AMC trial are updated nightly on the password-protected section of the AMC web site. The progress of each AMC trial is reviewed regularly by the Protocol Chair and also by the appropriate disease-oriented Working Group during scheduled conference calls. For phase I dose escalation trials, dose escalation (or dose de-escalation) is based on the rules in the protocol and the Protocol Chair, AMC Medical Monitor, and Group Statistician determine whether these criteria have been met. For phase II trials, stopping the trial for toxicity or efficacy, or suspending enrollment pending observation of responses in a multi-stage phase II trial, is based on meeting criteria stated in the protocol, and the Protocol Chair, AMC Medical Monitor, and Group Statistician determine whether these criteria have been met.

For phase III trials, the AMC has formed an independent Data Safety and Monitoring Board (DSMB). Voting members of the DSMB are physicians, a statistician, and a patient advocate. All voting members are from outside the AMC. Nonvoting members are the AMC Group Statistician, the Statistician listed on the protocol, an AMC Operations Center staff member, two representatives (normally a clinician or

statistician) from the Office of HIV AIDS Malignancy (OHAM) or from the Cancer Therapy Evaluation Program, Division of Cancer Treatment and Diagnosis, of the National Cancer Institute (NCI). The AMC Data Safety and Monitoring Board reviews AMC phase III studies in accordance with the National Cancer Institute's Policy for Data Safety and Monitoring. Confidential reports of all phase III trials are prepared by the AMC Group Statistician with support from the AMC ODMC. A written report containing the current status of each trial monitored, and when appropriate, any toxicity and outcome data, are sent to DSMB members by the AMC ODMC within the timelines specified by the AMC DSMB Charter. This report addresses specific toxicity concerns as well as concerns about the conduct of the trial. The report may contain recommendations for consideration by the DSMB concerning whether to close the trial, report the results, or continue accrual or follow-up.

The results of each DSMB meeting are summarized in a formal report sent by the DSMB Chair to the Group Chair and AMC ODMC. The DSMB report contains recommendations on whether to close each study reviewed, whether to report the results, and whether to continue accrual or follow-up. A primary recommendation (e.g., continue with no change; recommended or required modification; stop) must be included in the document. The Group Chair is then responsible for notifying the Protocol Chair and relevant Disease-oriented Working Group Chair before the recommendations of the DSMB are carried out. In the unlikely event that the Protocol Chair does not concur with the DSMB, then the NCI Division Director or designee must be informed of the reason for the disagreement. The Study Chair, relevant Disease-oriented Working Group Chair, Group Chair, DSMB Chair, and NCI Division Director or designee will be responsible for reaching a mutually acceptable decision about the study. CTEP approval of a formal amendment will be required prior to any implementation of a change to the study.

Following a DSMB meeting, a summary of the serious adverse events reported to the DSMB is posted to the AMC web site. It is each site's responsibility for conveying this information to its IRB.

#### **Plans for Assuring Compliance with Requirements Regarding the Reporting of Adverse Events (AE)**

For trials monitored by the NCI's Clinical Data Update System (CDUS), adverse event information is transmitted electronically to NCI on a quarterly basis. For trials monitored by NCI's Clinical Trials Monitoring Service (CTMS), adverse event information is transmitted electronically to NCI every two weeks.

The Protocol Chair, AMC Group Chair, and the AMC ODMC share responsibility in assuring that participating investigators comply with the protocol requirements for adverse event reporting. All AMC investigators certify compliance with NCI and FDA requirements for adverse event reporting by signing the AMC Adherence Statement for site membership, the protocol signature page for each protocol active at the site, and Form FDA-1572 for CTEP investigator registration and IND studies sponsored by AMC investigators. Investigators are responsible for identifying and reporting all adverse events to the AMC ODMC, AdEERS, and/or sponsors according to the protocol requirements, and assuring compliance with reporting to the local IRB. Protocol compliance with adverse event reporting requirements is assessed by the AMC ODMC during routine site monitoring visits by reviewing the site's source documentation.

The data entry system used for AMC studies, AdvantageEDCSM (a web-based data entry and enrollment system), is programmed to notify the site investigator, protocol chair, and AMC ODMC via email in the event that a site reports an adverse event that meets expedited reporting criteria to NCI and/or FDA. If the site does not follow with an AdEERS report, the AMC ODMC contacts sites to request an expedited report. Additionally, the protocol chair, AMC ODMC, and the AMC Medical Monitor review reported adverse events on a routine basis to identify adverse events reported by sites that require expedited reporting via AdEERS. The Protocol Chair, AMC Group Chair, and IND sponsors have general

oversight for assuring that routine and expedited adverse reporting requirements are met by the responsible parties.

### **Plans for Assuring that any Action Resulting in a Temporary or Permanent Suspension of an NCI-Funded Clinical Trial is Reported to the NCI Grant Program Director Responsible for the Grant**

In the event that termination of the trial or major modification to the protocol is under consideration, the Protocol Chair will convene the AMC Data Coordinator and Disease-oriented Working Group Chair by conference call to discuss the options. For phase I and II trials, the Protocol Chair also has the option of asking the AMC DSMB to review the study. The AMC ODMC will inform the CTEP Protocol Information Office (PIO) when studies are temporarily or permanently closed. The Cancer Treatment and Evaluation Program (CTEP) of the National Cancer Institute (NCI) must approve all protocol amendments prior to distributing to the AMC sites.

### **Plans for Assuring Data Accuracy and Protocol Compliance**

All study data for AMC clinical trials are entered directly by AMC site staff into AdvantageEDCSM. During data entry, the system performs validation checks on many fields and performs consistency checks between select fields. Range checks are placed on each field to eliminate entry of out-of-range values. Edit check programs are run on the database on a set schedule to identify and resolve inconsistencies between forms or data collected at different points in time. AMC ODMC staff routinely interacts with site staff to resolve any data problems.

In accordance with NCI guidelines, the AMC ODMC conducts monitoring visits at the AMC sites to evaluate compliance with regulatory issues, and to review data for specific cases by checking source documents. These reports are sent to the site Principal Investigator and to the NCI. In the event that major violations are identified, sites are asked to provide a plan to correct deficiencies within 30 days. If needed, a repeat site visit is conducted. In the event that a site does not correct deficiencies in a pre-determined time frame, the AMC Executive Committee has the option of taking action against the site. Possible actions include, but are not limited to, suspending enrollment of new patients to AMC trials until deficiencies are corrected; recommending a decrease in funding to the site; and requiring specific training for site investigators or staff members.

**APPENDIX XI: PATIENT STUDY DRUG COMPLIANCE LOG**

PROTOCOL NUMBER: AMC-059	Patient Study Drug Compliance Log Cycle __
Site ID _____ Subject ID: 059 -____-____	Subject's Initials _____

Planned Dose (number of pills to be taken per dose)		
Morning Dose	Afternoon Dose	Evening Dose

**Patient Instructions:** Please fill in the calendar dates and enter the number of PTC299 pills actually taken at each dosing time on each day. If a particular dose is missed, please write '0' in the column of that dose. When writing the date, please record in the dd/mmm/yyyy format (e.g., 15/Nov/2007).

Day	Date (dd/mmm/yyyy)	Morning Dose	Afternoon Dose	Evening Dose
1	___/___/20__			
2	___/___/20__			
3	___/___/20__			
4	___/___/20__			
5	___/___/20__			
6	___/___/20__			
7	___/___/20__			
8	___/___/20__			

PROTOCOL NUMBER: AMC-059	Patient Study Drug Compliance Log Cycle __
Site ID _____ Subject ID: 059 -____-____	Subject's Initials _____

Day	Date (dd/mmm/yyyy)	Morning Dose	Afternoon Dose	Evening Dose
9	___ / ___ / 20__			
10	___ / ___ / 20__			
11	___ / ___ / 20__			
12	___ / ___ / 20__			
13	___ / ___ / 20__			
14	___ / ___ / 20__			
15	___ / ___ / 20__			
16	___ / ___ / 20__			
17	___ / ___ / 20__			
18	___ / ___ / 20__			
19	___ / ___ / 20__			
20	___ / ___ / 20__			

PROTOCOL NUMBER: AMC-059	Patient Study Drug Compliance Log Cycle __
Site ID _____ Subject ID: 059 -____-____	Subject's Initials _____

Day	Date (dd/mmm/yyyy)	Morning Dose	Afternoon Dose	Evening Dose
21	___ / ___ / 20__			
22	___ / ___ / 20__			
23	___ / ___ / 20__			
24	___ / ___ / 20__			
25	___ / ___ / 20__			
26	___ / ___ / 20__			
27	___ / ___ / 20__			
28	___ / ___ / 20__			

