### 5.3.3 Definitions of Dose-Limiting Toxicity

The occurrence of DLTs during cycle 1 will be used to define the MTD. In cycle 1 and in subsequent cycles the occurrence of DLTs will determine the need for dose interruptions or reductions.

DLT will be defined as the occurrence of any of the following:

- Grade  $\geq 2$  PTC299-related vomiting despite maximal oral antiemetic therapy, or a requirement for intravenous (IV) antiemetics to control PTC299-related nausea and vomiting
- Grade  $\geq 2$  proteinuria

- In patients not receiving atazanavir or indinavir, change in total serum bilirubin from baseline value of Grade 0 to on-treatment value of Grade  $\geq 3$  ( $>3.0 \times \text{ULN}$ ), whether or not serum ALT or AST are elevated
- In patients receiving atazanavir or indinavir, on-treatment serum direct bilirubin  $>40\%$  of total bilirubin, whether or not serum ALT or AST are elevated
- Change in serum ALT or AST from baseline value of Grade 0 to on-treatment value of Grade  $\geq 2$  ( $>2.5 \times \text{ULN}$ )
- Change in serum ALT or AST from baseline value of Grade 1 to on-treatment value of Grade  $\geq 3$  ( $>5 \times \text{ULN}$ )
- Grade  $\geq 3$  PTC299-related toxicities (for purposes of defining the DLT, only toxicities considered by the investigator to be possibly, probably or definitely related to PTC299 will be considered).
- Failure to complete  $\geq 80\%$  of the planned 56 doses (i.e.,  $\geq 45$  doses) of a PTC299 treatment course due to PTC299-related toxicities.

Toxicities will be graded according to the CTCAE, Version 3.0. If multiple toxicities are seen, the presence of DLT will be based on the most severe toxicity experienced. At the end of each cycle, each subject must be assessed by the investigator as to whether or not the subject experienced DLT, and this information must be recorded on the Adverse Event CRF.

NOTE: If DLT is based on PTC 299-related increases in serum triglycerides or cholesterol, the increase must be confirmed in the fasting state and the grade of toxicity must be at least one grade higher than the baseline value.

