#### 5.3.4 Study Drug Dose Interruptions and Dose Modification for Toxicity

Subjects on a BID PTC299 treatment schedule who inadvertently have a delay in administration of a dose of the study drug of  $< 6$  hours should take the planned dose as soon as possible after the intended time of administration. For subjects who inadvertently have a delay in administration of study drug of  $\geq 6$  hours, the dose should not be taken. Study drug administration may continue but the missed dose should not be made up and the planned timing of subsequent study drug dosing should not be altered.

For subjects on a TID PTC299 treatment schedule who inadvertently have a delay in administration of a dose of the study drug of  $\leq 1$  hour, the planned dose should be taken with no changes to the subsequent dose schedule. For subjects who have a delay of  $>1$  hour but  $\leq 4$  hours, the planned dose should be taken; however, all future doses for that day should be shifted later by a corresponding amount. It is recommended that subjects take the last dose of study medication no later than 12:00 midnight on any study treatment day. For example if the 07:00 AM dose is taken at 10:00 AM, the next dose should be taken at 5:00 PM, and the last dose should be taken at 12:00 midnight. For subjects who have a delay in administration of study drug of  $>4$  hours, the dose should not be taken. Study drug administration may continue but the missed dose should not be made up and the planned timing of subsequent study drug dosing should not be altered.

Vomiting upon dose administration is considered as a missed dose; the dose should not be made up and the planned timing of subsequent study drug dosing should not be altered.

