### 5.5 Treatment Compliance

Records of study medication used, dosages administered, and intervals between visits will be kept during the study. Drug accountability will be noted at the completion of the trial. Subjects will be asked to return all unused medication at the monthly visits.

Subjects will also be given a diary to carry home and will be instructed to record each time study drug is administered. The subject will be asked to bring the diary to each clinic visit (see Appendix XI).

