Immunohistochemistry (IHC) will be used to determine expression of the following: VEGF, VEGFR-2, VEGFR-3, phospho-Akt, KSHV LANA, orf59, p53 and HIF-1 $\alpha$ . We will count the number of positive cells per HPF for a total of 10 fields per section and derive an index value. We will consider a 50% change from baseline in the index value for the aforementioned markers a biological response. For each measure (VEGF, VEGFR-2, VEGFR-3, phospho-Akt, KSHV LANA, orf59, p53 and HIF-1 $\alpha$ ), we will estimate the proportion of patients who demonstrate a 50% change between baseline and on treatment (between day 22 and day 28) value. The exact binomial 95% confidence interval will be derived for each measure.

To evaluate the effects of PTC299 on tumor cell proliferation, the change in immunohistochemistry of Ki67 from the pre-treatment to the post-treatment biopsy will be tested using the Wilcoxon sign test to determine if the change is less than zero, suggesting a decrease. To evaluate the drug's effects on circulating concentrations of angiogenic factors and cytokines, HIV and KSHV loads, and T-lymphocyte subsets, changes in these levels from pre-treatment to indicated sampling times will be tested by repeated-measures ANOVA, single and multivariate analysis.

For each subject, study drug administration will be described in terms of the actual doses administered and the proportion of drug actually delivered relative to the amount that should have been delivered. The total number of cycles administered; the median (range) of cycles administered; dose modifications, dose delays, and dose omissions; and reasons for deviations from planned therapy will be described by starting dose level. The type and timing of use of concomitant drugs will also be described.

AEs and laboratory abnormalities will be summarized by type and severity grade. First-cycle DLTs, adverse events leading to death or to discontinuation from treatment, and serious adverse events will be considered with special attention.

Pharmacokinetic parameters will be calculated using the actual sample collection times. Pharmacokinetic variables will be calculated from the plasma concentration data using standard compartmental and noncompartmental methods, as appropriate for the data. Variables of interest may include  $T_{max}$ ,  $C_{max}$ ,  $C_{24h}$ ,  $AUC_{0-24}$ , and  $t_{1/2}$ . Plasma concentrations and PK parameter results will be presented in tabular and graphic form by dose level and

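### The patient log cannot mark a vomited dose, which Section 5.3.4 counts as missed, so delivered dose may be overstated and the 80% completion count may be too high

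*Combined protocol and SAP*

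**What the plan says.** Five places bear on how a vomited dose is counted.

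- **Section 5.3.4** sets the counting rule: "Vomiting upon dose administration is considered as a missed dose". Such a dose is not made up.
- **Appendix XI**, filled in by the patient, asks the patient to "enter the number of PTC299 pills actually taken at each dosing time on each day". Its next sentence reads: "If a particular dose is missed, please write '0' in the column of that dose". The log does not mention vomiting, does not define a missed dose, and has no column for a mark or a reason.
- **Section 5.5** says that subjects "will be instructed to record each time study drug is administered", and that unused drug is returned at the monthly visits.
- **Section 5.3.3** makes it a DLT to complete less than 80% (fewer than 45 of 56 doses) "of a PTC299 treatment course due to PTC299-related toxicities". First-cycle DLTs define the MTD. The investigator decides at the end of each cycle whether a DLT occurred and records it on the Adverse Event CRF.
- **Section 11.2** promises to describe, for each subject, "the proportion of drug actually delivered relative to the amount that should have been delivered". It names no data source and no rule for vomited doses.

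**The concern.** In ordinary language, capsules that were swallowed and then vomited were taken. A patient who has not been told the protocol's meaning of a missed dose can reasonably enter the full number. Another patient, or a site that applies Section 5.3.4, would enter 0. The same event may then be recorded in two ways.

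The other records described do not recover the count:

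- Returned capsules (Sections 5.2.3 and 5.5) treat a vomited capsule as taken.
- Clinic staff record only doses given in the clinic or hospital (5.2.3). In cycle 1, Section 5.3.1 specifies clinic dosing only on Days 1 and 28.
- For adverse events, Section 6.3 asks for all grades on the CRF, while Section 4.0 requires CRF recording of symptoms only from Grade 2 and only if clinically significant or drug-related. Neither asks how many doses were lost.

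Two outputs depend on the count. One is the delivered-dose summary in Section 11.2. The other is the 80% completion criterion, which feeds the MTD (a primary objective) in cycle 1 and the dose-modification rules in later cycles. If the information is not captured at the time, it cannot be rebuilt afterwards.

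**Working it through.** **Inputs.** Planned doses per 28-day cycle: 56 (BID) to 84 (TID), Section 5.3.1. Completion threshold: 80% of 56, stated as at least 45 doses, Section 5.3.3. Vomited doses count as missed, Section 5.3.4.

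**1. The plan's own figure.** 0.80 × 56 = 44.8, rounded up to 45. This reproduces Section 5.3.3. The criterion is met at 56 − 45 + 1 = 12 lost doses: 44/56 = 78.6%, against 45/56 = 80.4% with 11 lost.

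**2. Delivered dose.** Let v be the number of vomited doses entered as taken, with the dose level unchanged through the cycle. The proportion delivered is overstated by v/56 (BID) or v/84 (TID).

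| v | BID overstatement | TID overstatement |
|---|---|---|
| 1 | 1/56 = 1.8 points | 1/84 = 1.2 points |
| 3 | 3/56 = 5.4 points | 3/84 = 3.6 points |
| 6 | 6/56 = 10.7 points | 6/84 = 7.1 points |

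No threshold has to be crossed for this to occur.

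**3. Completion DLT, 56-dose cycle.** Let m be the other toxicity-related misses, correctly entered as 0, and let all v vomited doses be drug-related. The true loss is v + m and the logged loss is m. A classification based on the log alone is wrong when v + m ≥ 12 and m ≤ 11, that is, when m lies between max(0, 12 − v) and 11.

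| v | m for which the classification changes |
|---|---|
| 1 | 11 only |
| 3 | 9 to 11 |
| 6 | 6 to 11 |
| 12 | 0 to 11 |

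With v = 12 and m = 0, the subject has completed 44/56 = 78.6% under Section 5.3.4, while the log could show 56/56 = 100%.

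**4. 84-dose cycle.** Section 5.3.3 gives only the 56-dose figures. If the 80% is scaled (an assumption), 0.80 × 84 = 67.2, so 68 doses are needed and 17 losses meet the criterion (67/84 = 79.8%). If 45 doses were applied literally, it would take 84 − 44 = 40 losses (44/84 = 52.4%). The documents do not say which applies, so the sections need reconciling on this as well.

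**5. Which vomiting is left to this criterion.** Section 5.3.3 separately makes a DLT of drug-related vomiting of Grade 2 or higher that persists on maximal oral antiemetics, of a need for IV antiemetics, and of any drug-related toxicity of Grade 3 or higher. Only vomiting below those criteria depends on the dose count.

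**The case against.** The strongest reply is that nothing on the page conflicts. The log says to write 0 for a missed dose, and Section 5.3.4 says that a vomited dose is missed, so the two together give 0. The rule against making up a vomited dose governs behaviour at home, which suggests that patients are told about it, and Section 5.5 says they receive diary instruction. This stands in part. A reader might infer that the log contradicts Section 5.3.4 or directs patients to enter vomited doses as taken; it does neither. The form is ambiguous. The content of the diary instruction is not given in the text reviewed, and the printed log carries none of the rule.

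Second, the log is not named as the source for the DLT decision. The investigator also has the symptom review and toxicity evaluation at Day 15 and Day 29, the adverse event records, and the concomitant drugs with reasons for use, which would include antiemetics. This also stands: it cannot be said that vomited doses drop out of the DLT assessment. Yet none of those records is asked to give a number of lost doses, and the 80% criterion needs one.

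Third, Section 11.2 plans to describe dose omissions and the reasons for deviations, so reasons may be collected on a CRF. The CRFs are not in the text reviewed, and the absence of a reason column in the log does not show that the trial collects no reasons.

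Fourth, vomiting that costs 12 of 56 doses may well already meet another DLT criterion, and Section 5.4 suggests antiemetics from Grade 1. That limits how often the completion criterion would be affected.

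**Conclusion.** The point holds as a gap between a stated counting rule and the only dose-by-dose record of home dosing that the documents describe. Vomited doses may be recorded as taken, and returned capsules cannot reveal it. Delivered dose is the more exposed output: 1.8 points per such dose on BID and 1.2 on TID. The completion DLT is affected only if the log drives the count and at least 12 of 56 doses are lost through lower-grade vomiting, alone or with other toxicity-related misses. That is probably uncommon.

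A reader might go further and infer a biased MTD, putting a reduced DLT rate into the escalation probabilities of Table 6. That would require the share of DLTs arising only by this route, and the documents give no such figure. The healthy-volunteer summaries (1.2.6.1 and 1.2.6.2) report nausea but do not list vomiting, and Section 5.3.6 reports no drug-related adverse events in 12 cancer patients (six at each of two doses). No shift in escalation probability can be quantified. Nor do the documents support a claim that response by dose would be distorted: Section 11.2 plans no analysis of response by delivered dose, and exposure is measured by plasma PK.

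The change is worth making because it is cheap and the data cannot be recovered later. The result rests on two assumptions: that some patients enter what they swallowed, and that the dose level is constant within the cycle.

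**What to change.** Reconcile Appendix XI with Section 5.3.4:

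1. Add to the log a mark for a dose vomited upon administration, keeping to the scope of 5.3.4's own wording. An instruction covering any vomiting after a dose would be wider than the rule. If time is needed to decide whether an episode falls under 5.3.4, record the time of vomiting.
2. Add a short reason for each missed or vomited dose, unless the CRF already collects it. The completion criterion counts only losses from drug-related toxicity.
3. State in Sections 5.3.3 and 11.2 that marked doses are counted as 5.3.4 already defines, and name the data source for the completion criterion and for the proportion delivered.
4. Reconcile the 56-dose figures in 5.3.3 with the 84-dose cycles in 5.3.1.

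This alters no dose or clinical rule and needs no extra visits or patients. It costs a revised diary page, possibly one CRF code, a sentence in each of the two sections, and slightly less favourable delivered-dose figures. Section 3.3.1 says that Stages 1 and 2 are already enrolled, so the mark helps only cycles not yet completed, and the report should say so when it presents delivered dose.
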